# **Background and Introduction**

In order to reduce our nation's persistently elevated rate of unplanned pregnancy we must seek every opportunity to provide women who desire contraception with the most effective methods. The vast majority of the 3.1 million unintended pregnancies in the U.S. each year result from situations where contraception was used imperfectly or not at all. Unfortunately, the wide availability of oral EC pills has not reduced abortion rates. Providing non-users and users of less effective methods of contraception with highly effective contraception is an efficient strategy to reduce rates of unplanned pregnancy and abortion. Application of this principal has reduced repeat abortions for women who receive immediate post-abortal IUD insertion. Like women seeking abortion, EC users are at high risk of unplanned pregnancy and are making a conscious effort to acutely reduce that risk.

The demand for EC confirms a tremendous unmet public health need for more reliable and more effective contraception. The copper IUD is the most efficacious method of EC (pregnancy rates of 0.1%)[1] and offers continued highly effective contraception for over a decade. While its use is supported by a Cochrane Review, ACOG, and several other professional organizations and authors, it is rarely used. While the copper IUD for EC has advantages over oral EC pills, U.S. women selecting IUDs outside of the EC setting have shown a strong preference for the LNG IUD as it minimizes or eliminates menstrual bleeding and discomfort.[2, 3]. The Contraceptive CHOICE project  illustrates this. Of the 9,256 women enrolled in this prospective cohort who were provided with their contraceptive method of choice without cost 47% of participants selected the LNG IUD and 9% the copper IUD. We are unaware if offering women the option to receive either IUD method will increase uptake of highly effective methods by EC users.

Offering women presenting for EC the option of the LNG or copper IUD may increase the initiation of highly effective methods of contraception among a population at high risk of unintended pregnancy. Leaders in the field of EC, acknowledging the lack of effect of increasing availability to EC pills on reducing rates of unplanned pregnancy, have called for procedures that streamline the delivery of highly effective methods of contraception when women present for EC.

Our research team working in conjunction with our clinical partners at Planned Parenthood Association of Utah (PPAU) have conducted several studies evaluating use of the IUD in women presenting for EC. The cumulative findings of our research to date show that EC users are willing to have the copper IUD placed[4, 5] and those that obtain it have lower pregnancy rates than those choosing oral LNG for EC.[6] Our recent study assessing the LNG IUD with oral LNG for EC users has shown no pregnancies with 110 women using this approach. In addition, 90% of participants agreed to being randomized to either type of IUD. The potential to further reduce unintended pregnancy in a high risk population by offering the preferred method of IUD supports a randomized controlled trial of the copper and LNG IUDs for EC users.

Study Design:

Protocol Summary (ERICA) Page **2** of **12**  Non-inferiority randomized controlled trial. If recruitment is not adequate with this design and potential participants report concern about randomization as a reason for non-participation then a patient-preference cohort (PPC) will be offered to interested and qualified individuals.

All women presenting to participating clinics when study participation is offered will be presented with a study information sheet (discussed below) which includes an assessment of interest in the study. If we find that we are not able to meet recruitment goals (e.g. <80 participants enrolled in the first 6 months) and the reason for non-participation is assessed to be lack of willingness to be randomized to the study interventions, then we will add an option for a PPC. Should the PPC be introduced then participants who are interested in the study and eligible for participation but not willing to be randomized will be offered participation through the PPC which has a separate consent form. While 90% of EC users enrolled in a current study where they can choose their IUD type stated they would be be willing to be randomized to either type of IUD, some individuals may be reluctant to agree to random assignment. This potentially impacts result generalizability. In order to evaluate the magnitude and direction of non-participation bias we will offer eligible women presenting for EC who desire an IUD but are not willing to undergo randomization participation in a patientpreference cohort (PPC). Participants in the PPC may choose the IUD they desire. Based on our survey of current participants in an EC Trial offering women the copper IUD or the LNG IUD and oral LNG we expect that the significant majority of potential participants in this trial will agree to randomization. The PPC will allow us to ascertain selection bias due to RCT nonparticipation. We will evaluate participant demographics and clinical characteristics. This strategy has been successfully used the OPUS trial, an RCT assessing a mid-urethral sling or sham incisions at the time of pelvic organ prolapse repair.[7]

# **Purpose and Objectives**

In this prospective observational study, all women presenting for Emergency Contraception (EC) at Planned Parenthood Association of Utah (PPAU) clinics will be counseled using a standardized script; those interested in an IUD, who meet study qualifications and agree to participate, will be randomized to either the hormonal IUD (LNG 52mg IUD commonly known as Mirena® or Lilleta®) or the copper IUD (Paragard®). Participants will be followed for one year. If enrollment goals are not achieved due to a lack of willingness among potential participants to be randomized then we will initiate a PPC (patient preference cohort). In that case, participants who are interested in the study and eligible for participation but not willing to be randomized will be offered participation in a PPC.

This study has three specific objectives.

**Objective 1**: Determine the efficacy of the levonorgestrel IUD and copper T380 IUD for emergency contraception as assessed by urine pregnancy tests 1 month after EC use.

*Hypothesis*: The LNG IUD is non-inferior to the copper T380 IUD for EC based on a 1% non-inferiority limit.

**Objective 2**: Compare the one-year unintended pregnancy rates from women initiating the levonorgestrel IUD vs. copper T380 IUD for EC.

*Hypothesis*: At one-year the LNG IUD users will have lower pregnancy rates compared to copper IUD users.

**Objective 3:** Assess the one-year continuation, satisfaction, pain, and bleeding patterns of a LNG20 IUD to a copper T380 IUC as a method of EC and the mechanisms of continuation.

*Hypothesis*: The LNG IUD will have superior rates of continuation and non-inferior satisfaction (what about pain and bleeding patterns) compared to the copper IUD as a method of EC and the mechanisms of continuation.

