# Statistical Methods, Data Analysis and Interpretation

**Sample Size and Randomization:** There are two arms to the study. The main study is a randomized controlled trial with non-inferiority design and participants will be assigned 1:1 to either the copper T380 IUD or the LNG20 IUD for EC. The non-inferiority margin is 2.5% and we assume a pregnancy rate of 0.1% for copper IUD EC users and a 1% EC pregnancy rate for LNG IUD users. This estimate, based on our current COLIEC study (IRB# 50483) is conservative, falling within the 95% confidence interval (CI) of 0%-5.2% of the pregnancy rate of LNG20 IUD plus oral LNG for EC users. To achieve 80% power to detect a twosided 95% CI around the EC pregnancy incidence, a percent difference that does not cross the 2.5% noninferiorty margin, will require 335 participants per study arm (total of 670). We will recruit an additional 5%, 36 participants, (total of 706) to accommodate for potential early loss to follow up. Five percent is a conservative estimate based on our prior successful IUD EC studies. Even with obtaining multiple points of contact information and testing them prior to enrollment this can be a difficult population to maintain contact with. In our prior EC studies at 1 month we lost contact with 12 of 218 (5.5%) IUD users in our copper T IUD vs. oral LNG study and 8 of 176 (4.5%) in the COLIEC study. The use of the 2.5% noninferiority margin is within confidence intervals of previous literature for pregnancies among oral LNG users, which is one of the clinical standards of care (1.7%; 95% CI 0.8%-2.6%) (76) and the continued protection against future unintended pregnancy explored in aim 2 makes this clinically acceptable. In addition, women who currently present for EC and decline a copper IUD are left with a choice of oral EC, which also falls within this confidence interval. While approaching the higher limit of the oral LNG per cycle pregnancy rate from the aforementioned study, it is well below per cycle pregnancy events in some subpopulations using oral LNG, which can result in pregnancy events of 5.8% for women with higher BMIs (>30BMI) and 7.3% in women who have additional unprotected sexual intercourse(28). The LNG20 IUD is not affected by BMI and offers protection against pregnancy following future intercourse.

The maximum number of participants in the entire study is 706.

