### Data Analyses:

The primary objective will be tested by non-inferiority design to test the hypothesis that the LNG IUD is no worse than the copper IUD with a noninferiority margin of 2.5%. Using Blackwelder's approach for equivalence testing,[8] comparing those who become pregnant during the menstrual cycle in which their study IUD was inserted. Noninferiority will be established if the lower bound of a two-sided 95% CI does not cross the noninferiority bound. Analysis will be by intention to treat.

For objective #2, comparison of one-year unintended pregnancy rates from women initiating the levonorgestrel IUD vs. copper T380 IUD for EC, will be assessed by Kaplan-Meier estimates. This same approach will be utilized to construct estimates of the proportion of patients who continue with their selected IUD for 1 year (continuation

proportion). Continuous variables will be assessed by t-tests and discrete variables by Chisquare testing as appropriate.

All data will be analyzed using Stata statistical software (College Station, Texas). Standard quality control methods will be employed including use of an independent data safety monitor.

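### Objective 1 sets a 1% non-inferiority limit for the primary comparison, while the sample size and the decision rule use 2.5%, and nothing reconciles them.

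*Combined protocol and SAP*

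**What the plan says.** Three places in the combined protocol and SAP set the limit for the primary comparison, EC pregnancy with the LNG IUD against the copper IUD about a month after insertion.

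- **Purpose and Objectives, Objective 1 (hypothesis):** "The LNG IUD is non-inferior to the copper T380 IUD for EC based on a 1% non-inferiority limit".
- **Statistical Methods, Sample Size and Randomization:** "The non-inferiority margin is 2.5% and we assume a pregnancy rate of 0.1% for copper IUD EC users and a 1% EC pregnancy rate". The second of these rates is the one assumed with the LNG IUD. The target of 80% power is tied to "a percent difference that does not cross the 2.5% noninferiorty margin, will require 335 participants per study arm (total of 670"). The section also argues for this limit: "The use of the 2.5% noninferiority margin is within confidence intervals of previous literature for pregnancies among oral LNG users".
- **Data Analyses (primary objective):** the hypothesis tested is that "the LNG IUD is no worse than the copper IUD with a noninferiority margin of 2.5"%, with the rule "Noninferiority will be established if the lower bound of a two-sided 95% CI does not cross the noninferiority bound".

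All three are current text. The sample-size section does not mention a 1% limit. The 1% that it does contain is the assumed LNG pregnancy rate, not a margin.

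**The concern.** A non-inferiority trial has one margin, and that margin decides the primary conclusion. Here the hypothesis carries one value and the sizing and decision rule carry another. Moving between the pregnancy and no-pregnancy scales reverses the sign of a risk difference but not its size, so 1% and 2.5% cannot be the same limit expressed in two ways.

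If the upper 95% limit for the LNG minus copper pregnancy rate falls between 1% and 2.5%, the trial meets the rule in Data Analyses and fails the hypothesis in Objective 1. A reader could hold it to either. If the choice is made after results by arm are known, taking the looser limit will look data-driven, and the protocol's own hypothesis can be cited against the claim.

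**Working it through.** **Inputs, all from the plan.** Pregnancy rates: copper 0.001, LNG 0.01, so an assumed difference of 0.009. Power 80%. Two-sided 95% CI, that is one-sided 0.025. Allocation 1:1. Stated N: 335 per arm, 670 in total, 706 after the allowance for loss.

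**Reproducing the plan's N (2.5%).** Unpooled formula: n per arm = (1.960 + 0.842)² × [p_C(1 − p_C) + p_L(1 − p_L)] / (margin − difference)².

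- Variance sum: 0.001 × 0.999 + 0.01 × 0.99 = 0.010899
- Squared normal quantiles (unrounded): 7.84888
- n = 7.84888 × 0.010899 / (0.025 − 0.009)² = 334.2, rounded up to **335**, as stated
- Allowance for loss: 670 / 0.95 = 705.3, rounded up to **706**, as stated

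A one-sided alpha of 0.05 gives 264 and does not match. The stated N therefore rests on 2.5% with one-sided 0.025.

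**Same formula at 1%.** n = 7.84888 × 0.010899 / (0.010 − 0.009)² = **85,545 per arm**. The number is this large because the assumed difference uses up 0.9 of the 1.0 point, leaving 0.1 point; at 2.5%, 1.6 points are left. It is very sensitive to the assumed LNG rate. With both rates at 0.1%, the formula gives 157 per arm, though the normal approximation is poor there.

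**Power at 335 per arm, planning rates.** SE = √(0.010899 / 335) = 0.005704.

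- Formula, 2.5%: Φ(0.016 / 0.005704 − 1.96) = 0.801
- Formula, 1%: Φ(0.001 / 0.005704 − 1.96) = 0.037

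The plan cites Blackwelder's approach but gives no interval formula. The exact binomial figures below therefore use two intervals, as an assumption. A pass means that the upper 95% limit of LNG minus copper is below the margin.

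| Method (335 per arm) | Passes 2.5% | Passes 1% |
|---|---|---|
| Planning formula | 80% | 3.7% |
| Exact, Wald | 76% | 15% |
| Exact, Newcombe | 42% | 1% |

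**Results on which the two limits disagree.** With 335 per arm and no copper pregnancies:

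| LNG pregnancies | Wald upper limit | At 2.5% | At 1% |
|---|---|---|---|
| 1 | 0.88% | pass | pass |
| 2 | 1.42% | pass | fail |
| 3 | 1.90% | pass | fail |
| 4 | 2.36% | pass | fail |
| 5 | 2.79% | fail | fail |

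**Probability of a split verdict** (passes 2.5%, fails 1%; copper rate 0.1%):

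| True LNG rate | 335 per arm, Wald / Newcombe | 353 per arm, Wald / Newcombe |
|---|---|---|
| 1% (planning rate) | 61% / 41% | 63% / 53% |
| 0.5% | 47% / 75% | 50% / 85% |
| 0.1% | 4.5% / 79% | 4.9% / 79% |

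The column for 353 takes all 706 recruited as evaluable. The low Wald figures in the last row partly reflect an interval of zero width when neither arm has a pregnancy. With Newcombe, 0 against 0 at 335 per arm gives an upper limit of 1.13%, which fails 1% and passes 2.5%.

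**The case against.** The strongest reply is that the 1% is leftover drafting. It appears once, with no rationale, sample size or rule attached. The same section still contains an unresolved drafting query about pain and bleeding patterns, and it calls this randomized trial observational. The sizing and the decision rule agree at 2.5%, so an analyst following Data Analyses would know what to do. That reading is plausible, and the analysis does stay workable. But it is an inference: the document gives no order of precedence, and the conflicting figure sits in the primary hypothesis.

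The figure of 85,545 per arm can also mislead if read as the general price of a 1% margin. This is fair. It holds only at the plan's assumed rates, and a sponsor who intended 1% would probably revisit the LNG rate, which the plan itself describes as conservative.

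The 3.7% power is an approximation, and exact enumeration with a Wald interval gives 15%. The split-verdict probabilities also move widely with the interval and the true rate. Both points are correct and are shown above. On none of these calculations is the planned N adequate for a 1% limit at the planning rates.

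**Conclusion.** The concern holds. Objective 1 states 1%; the sample size and the decision rule use 2.5% for the same comparison; nothing reconciles them. The sample size is not itself wrong, since 335 per arm follows from 2.5%. The error lies in the statement of the primary hypothesis, and it must be fixed because the margin is the criterion for the main conclusion.

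At the planning rates and 335 per arm, power at a 1% limit is between 1% and 15% depending on the method, and the chance that the two limits give different verdicts is 61% (Wald) or 41% (Newcombe). These figures assume the plan's rates and one of two intervals that the plan does not name. They also read the lower bound in Data Analyses as referring to the no-pregnancy scale, which is equivalent to the upper bound for LNG minus copper pregnancy; the plan does not state the scale or the direction of subtraction. The contradiction itself depends on none of these assumptions.

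**What to change.** The sponsor should confirm the intended margin and state one absolute value throughout, by a dated amendment made before outcome data by arm are seen.

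- **If 2.5% is intended**, as the design suggests: reword the Objective 1 hypothesis to an absolute non-inferiority margin of 2.5 percentage points (LNG minus copper EC pregnancy rate), and record that the 1% limit is superseded. This costs one line; N and the decision rule are unchanged. The drawback is a less strict stated hypothesis.
- **If 1% is intended:** redo the sample size and the margin rationale in Sample Size and Randomization, and the rule in Data Analyses. At the plan's assumed rates this needs about 85,545 per arm, which is out of reach for a trial of 706, so the assumed LNG rate would have to be re-examined as well.

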### 12 months after enrollment (return visit)

- Urine pregnancy test (Completed at the Planned Parenthood Clinic Lab).
- IUD string check.
- Review for potential adverse events.
- Review of bleeding experience, questionnaire review including unplanned pregnancy, abortion, sexual activity, IUD complications, contraception related side effects, participant clinic visits, use of condoms, employment status, income, school attendance, and satisfaction with contraception method.
- If participant cannot come to the clinic for their for 12-month visit, they will be contacted by a research assistant for review of follow-up information (bullet point #4 above) which can be completed via telephone, text, or email links to an online survey (based on participant preference). The study team will also provide participants with a urine pregnancy test they can take at home (if unable to come into the clinic for this final visit) and ask that participants send the results of the home-urine pregnancy test to the study team via email, phone or text.

**\*\***Note: We have provided specifics about the questionnaires/surveys that will be asked of participants under each of the study procedure sections. It is our understanding that we are not required to submit full versions of the surveys to the IRB, as long as we have provided thorough descriptions of what will be asked of participants.

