### Secondary Outcomes:

one-year unintended pregnancy rates

Assess the one-year continuation, satisfaction, pain, and bleeding patterns of a LNG20 IUD to a copper T380 IUC as a method of EC

- Pregnancy rates in the first year after presenting for EC
- Timing of IUD insertion relative to time in the menstrual cycle (pre-ovulatory, ovulatory, post-ovulatory)
- Unplanned pregnancy rates in the first year after presenting for EC
- Effect of IUD choice on vaginal bleeding assessed monthly by Pictorial Blood Assessment Chart
- Infections
- IUD continuation, expulsions, and removals through the first year after presenting for EC
- Satisfaction with EC method and contraception chosen
- Sexual satisfaction at baseline and through the first year after presenting for EC
- Frequency of unprotected intercourse since presenting for EC
- Use of contraception in the year following presentation for EC
- New diagnosis of any STI
- IUD related complications
- Abortion
- Contraception related side effects
- Use of a barrier method for prevention of sexually transmitted infections

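### Objective 3 hypothesises non-inferior satisfaction with the LNG IUD, but the plan gives satisfaction no margin or confidence-interval rule, only catch-all tests of no difference

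*Combined protocol and SAP*

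**What the plan says.** The hypothesis under Objective 3 (Purpose and Objectives) makes two different claims for the LNG IUD, superiority on continuation and non-inferiority on satisfaction: "The LNG IUD will have superior rates of continuation and non-inferior satisfaction (what about pain and bleeding patterns". The words in parentheses are a drafting query that was never resolved. The objective itself sets the time frame at one year: "Assess the one-year continuation, satisfaction, pain, and bleeding patterns of a LNG20 IUD to a copper T380 IUC as a method of EC".

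Data Analyses then does three things.

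- For the primary objective it sets a 2.5% margin and a decision rule: "Noninferiority will be established if the lower bound of a two-sided 95% CI does not cross the noninferiority bound".
- For one-year pregnancy and for continuation it uses Kaplan-Meier estimates.
- For everything else it says: "Continuous variables will be assessed by t-tests and discrete variables by Chisquare testing as appropriate".

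Satisfaction is not mentioned in that section. Secondary Outcomes lists "Satisfaction with EC method and contraception chosen" and, as a separate item, "Sexual satisfaction at baseline and through the first year after presenting for EC". The 12-month visit collects "employment status, income, school attendance, and satisfaction with contraception method". No response scale is given. The scale may be in the questionnaires, which are described but not reproduced: "It is our understanding that we are not required to submit full versions of the surveys to the IRB".

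**The concern.** The hypothesis and the only analysis that reaches it are of different kinds. Non-inferiority asks whether the LNG IUD could be worse by more than a stated amount. A t-test or chi-square test asks whether the arms differ at all. A significant result in favour of LNG would establish non-inferiority at any margin, but a non-significant result leaves the question open. A chi-square test on a satisfaction item with several levels is weaker still, because it does not give the direction of a difference.

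The plan therefore cannot answer its own hypothesis in the situation for which that hypothesis is written, namely similar satisfaction in the two arms. Any margin chosen after the results are known would carry little weight. What is at stake is a claim under one of the three specific objectives, not the primary conclusion.

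**Working it through.** **1. The plan's own sample size.** Sample Size and Randomization assumes pregnancy rates of 0.1% (copper) and 1% (LNG), a 2.5% margin, 80% power and a two-sided 95% interval.

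n per arm = [0.001×0.999 + 0.01×0.99] × (1.960 + 0.842)² / (0.025 − 0.009)² = 334.2, which rounds up to 335. Allowing for 5% loss, 670/0.95 = 705.3, rounded up to 706.

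Both stated figures reproduce. They concern pregnancy at one month. The documents give no margin, power or sample size for satisfaction.

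**2. Inputs for satisfaction.** From the documents: 335 per arm and 1:1 allocation. Assumed, because the documents give no figures: satisfaction scored as yes or no, 70%, 80% or 90% satisfied, margins of 5 and 10 percentage points, and a two-sided 5% test.

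**3. Formulas** (normal approximation). Let p be the proportion satisfied on copper, g the true LNG minus copper difference, n the number per arm and m the margin.

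- SE = √[p(1−p)/n + (p+g)(1−p−g)/n]
- Chance that the test of no difference significantly favours LNG = Φ(g/SE − 1.96)
- Chance that the lower limit of the 95% interval lies above −m = Φ((g+m)/SE − 1.96)

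**4. Arms truly equal (g = 0), n = 335.** The test of no difference favours LNG with probability Φ(−1.96) = 0.025, whatever p is. Example for the interval rule at p = 0.8: SE = √(2×0.8×0.2/335) = 0.0309; for m = 0.05, Φ(1.618 − 1.96) = 0.366.

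| p | SE | Test of no difference | Interval rule, 5 points | Interval rule, 10 points |
|---|---|---|---|---|
| 0.7 | 0.0354 | 0.025 | 0.292 | 0.806 |
| 0.8 | 0.0309 | 0.025 | 0.366 | 0.899 |
| 0.9 | 0.0232 | 0.025 | 0.578 | 0.991 |

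**5. LNG truly 5 points better (g = 0.05), n = 335.** The test of no difference supports the hypothesis with probability 0.306, 0.400 and 0.694 for p = 0.7, 0.8 and 0.9. The interval rule with a 5-point margin does so with probability 0.827, 0.927 and 0.999.

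**6. Fewer participants at one year.** The 335 was sized for one month. With equal arms and an assumed 300 per arm, the interval rule passes 27-53% of the time (5 points) and 76-98% (10 points). With 268 per arm, an assumed 20% loss, it passes 24-49% and 71-97%.

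**The case against.** The strongest reply is that Data Analyses never says a test of no difference will decide the satisfaction hypothesis. The sentence is a catch-all, qualified by appropriateness, and it follows text about other outcomes. A comparison of two means also yields a confidence interval, so the obstacle is the missing margin rather than the test. Most of this stands. Satisfaction is covered only by inference, and the gap is best described as the absence of a margin and rule. But the catch-all is the only analysis the document offers for satisfaction, and an interval helps only if there is a margin set in advance to compare it with. The 2.5% margin cannot be borrowed, because it is justified from pregnancy rates with oral LNG.

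A second reply is that the size of the problem rests on assumed rates, margins and test level. That is correct, and the interval-rule figures vary widely with them. The 2.5% figure depends only on the assumed two-sided 5% level and on the arms being equal.

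A reader might infer that the investigators mean to treat a non-significant difference as proof of non-inferiority. No section says so. Such a reading would be unsafe: under the assumptions above, with LNG truly 5 points worse, the test is non-significant 50-72% of the time at 335 per arm. That is a caution about a possible misreading, not a fault in the plan.

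Finally, the preference for the LNG IUD described in Background and Introduction might make superiority likely. It concerns women choosing a device outside the EC setting, not satisfaction after random assignment. Even a true 5-point advantage would be missed by the test 31-69% of the time.

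**Conclusion.** The point holds. The document hypothesises non-inferior satisfaction but gives no margin or decision rule for it, and the only analysis that reaches satisfaction can support the hypothesis only by showing LNG significantly better. With equal arms, support is about 2.5%, against 29-58% or 81-99% for an interval rule with a 5- or 10-point margin. The first figure assumes a two-sided 5% level; the others assume 70-90% satisfied, yes/no scoring and 335 per arm.

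It does not follow that the trial's main result is compromised: the primary analysis and sample size are unaffected. Nor can the plan be faulted for having no satisfaction scale, since that may be in the questionnaires. A scale would in any case supply neither a margin nor a rule. The change should be made, but it concerns a secondary objective.

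**What to change.** Choose one of two routes.

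1. Keep the non-inferiority claim. State that one-year satisfaction will be judged by the two-sided 95% confidence interval for LNG minus copper against a margin justified before outcome data by arm are seen. Name the scale, and say whether the outcome is satisfaction with the EC method or with the contraceptive method, since Secondary Outcomes covers both.
2. If no margin can be justified, drop the non-inferiority wording and report the difference with its 95% confidence interval. The documents offer no basis for a margin, so this may be the realistic choice.

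Either way, delete the query about pain and bleeding from the hypothesis.

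A separate, inexpensive improvement concerns sexual satisfaction, which is also listed at baseline. If it is scored as a continuous measure, compare the arms with adjustment for the baseline value (ANCOVA) in place of a plain t-test. The gain depends on the correlation with baseline, which the documents do not give.

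Cost: protocol and SAP wording, one confidence interval and, on the first route, the work of justifying a margin. Satisfaction with the contraceptive method is already collected at 12 months, so no visit or participant is added. The downside of the first route is that with a 5-point margin and equal arms the claim would still fail 42-71% of the time at 335 per arm (1 − 0.578 to 1 − 0.292), and more often with loss to follow-up by one year.
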